## 14.8 Overall survival

Analysis (Analysis Population)	Derivation	Statistical Analysis Methods	Missing data handling
Secondary endpoint: Overall Response (OS)			
Secondary analysis (ITT)	Time from first administration of study treatment to the date of death due to any cause	Kaplan-Meier estimates (product-limit estimates) will be presented together with a summary of associated statistics (median time, 3-, 6-, 9-, 12-, 24-month rate estimates) including the corresponding two-sided 95% confidence intervals. The confidence intervals for the median will be calculated according to Brookmeyer and Crowley (1982) and confidence intervals for the survival function estimates at above defined timepoints will be derived using the log-log transformation according to Kalbfleisch and Prentice (2011) (conftype=loglog default option in SAS Proc LIFETEST). The estimate of the standard error will be computed using Greenwood's formula.	
For alive participants, OS will be censored at last date known to be alive
 
The following dates will be considered to determine the last date known to be alive (dates past the data cut-off will be ignored by the derivation; details provided in body text):
 

• All participant assessment dates

• Start and end dates of anticancer therapies administered after study treatment discontinuation.

• AE start and end dates

• Last known alive date collected on the 'Subject Status / Survival Follow-Up' eCRF page (do not use follow up date)

• Study drug start and end dates

 
Date of discontinuation from the "Study Termination" eCRF page (do not use if reason for discontinuation is lost to follow-up or death)

**Overall survival (OS)** is defined as the time from first administration of study treatment to the date of death due to any cause:

OS = (date of event or censoring – date of the first dose + 1)/30.4375 (months).

For participants alive at the time of data cut-off date or who are lost to follow up, OS will be censored at the last date known to be alive. The date of event / censoring is defined in [Table 6](#).

**Table 6** Survival Event / Censoring

Survival Status	Date of event/censoring	Censoring
Participants alive or lost to follow-up before or at cut-off date	Last date known to be alive	Yes
Participants who died before or at cut-off date	Date of death	No

The following complete dates will be considered to determine the last date known to be alive. Only the ones among them that are before or at data cut-off and which are not imputed shall be used in the derivation:

- All participant assessment dates (blood draws [laboratory, PK], vital signs, performance status, ECG, tumor assessments, quality of life assessments)
- Start and end dates of anticancer therapies administered after study treatment discontinuation.
- AE start and end dates
- Last known alive date in “Subject Status / Survival Follow-Up” eCRF page (do not use the follow up date)
- Study drug start and end dates (including reinitiation of treatment)
- Date of discontinuation from the “Study Termination” eCRF page (do not use if reason for discontinuation is lost to follow-up or death)

Only dates associated with actual examinations of the participant reported in the eCRF will be used in the derivation. Dates associated with a technical operation unrelated to participant status such as the date a blood sample was processed will not be used.

Data collected after re-initiated treatment will be considered in the derivation of the last known to be alive date.

The analysis of OS time will be performed with a Kaplan-Meier method with the same approach as for PFS described in Section 14.4. Kaplan-Meier estimates (product-limit estimates) will be presented together with a summary of associated statistics including corresponding two-sided 95% CIs. OS rates with their CI at 3, 6, 9,12 and 24 months will be presented, as well as the number of participants at risk and failed. Censoring reasons will also be described. Censoring reasons are as follows:

- Alive at cut-off date
- Withdrawal of consent
- Lost to follow-up

OS will also be presented graphically with Kaplan-Meier figures.

A participant listing will provide the following information: participant identifier, age, sex, race, date of first study intervention, date of event/censoring, event/censoring reason, time to event.

### 14.8.1 Subgroup analysis for OS

Overall survival will also be evaluated on all subgroups as defined in Section 8.2. This will be repeated for Japanese participants including only the ADA and nAb status subgroup.

For the ADA and nAb subgroups, participant listings will provide the following information: participant ID, age, sex, race, ADA status, nAb PD-L1 assay status, nAb TGF- $\beta$  assay status, date of first administration, date of last tumor assessment, date of event/censoring, event/censoring reason, time to event. Two listings will be created: for the ADA positive participants and for nAb positive in either assay (PD-L1 and TGF- $\beta$ ) participants.

Participants with missing subgroup category will not be included in the related subgroup analysis. Those subgroups analyses will be supported by Kaplan-Meier and forest plots (based on OS rates at 6-month and 12-month).

### 14.9 Follow-up time (PFS)

Kaplan-Meier analysis will be performed to estimate median time of duration of follow-up for PFS as adjudicated by IRC using the reverse censoring indicator of the PFS analysis (see Section 14.4).

Kaplan-Meier survival curves will also be presented with median duration of follow-up and its two-sided 95% CI. In particular, the follow-up rates at 3, 6, 9, 12 and 24 months will be estimated with their 95% CI.

### 14.10 Follow-up time (OS)

Kaplan-Meier analysis will be performed to estimate median time of duration of follow-up for OS using the reverse censoring indicator of the OS analysis (see Section 14.8).

Kaplan-Meier survival curves will also be presented with median duration of follow-up and its two-sided 95% CI. In particular, the follow-up rates at 3, 6, 9, 12 and 24 months will be estimated with their 95% CI.

## 15 Safety Analyses

*Analysis set: SAF*

The subsections in this section include specifications for summarizing safety endpoints that are common across clinical studies such as adverse events, laboratory tests and vital signs.

### 15.1 Adverse Events

Treatment-emergent adverse events (TEAEs) are those events with onset dates occurring during the on-treatment period or if the worsening of an event is during the on-treatment period.

Changes in toxicity grade, seriousness or outcome of AEs are recorded as separate entries in the eCRF with associated end and start dates (start date equals end date of previous entry). Such entries reporting the same event in such immediately consecutive periods will be considered as one event in the analysis. These events will be kept as separate records in the database in order to maintain

the full detailed history of the events. The start date of the initial record in the sequence is taken as start date of the entire event, similarly the end date of the last event in the sequence is taken as end date of the entire event. The overall outcome of the adverse event is the outcome of the last event in the sequence. Duration of the AE and the TEAE flag will be adjusted accordingly in the analysis.

All analyses described in this section will be based on TEAEs if not otherwise specified. The AE listings will include all AEs. AEs outside the on-treatment period (prior or after) will be flagged in listings. AEs occurring during the re-initiation phase will be considered in the summary tables and will be flagged in listings.

Incomplete AE-related dates will be handled as stated in Section 9.

**Related Adverse Events** are those events with relationship to study treatment (as recorded on the “Adverse Events Details” eCRF page, Relationship with M7824= Related) reported by the Investigator and those of unknown relationship (i.e. no answer to the question “Relationship with M7824”).

**Serious Adverse Events (SAE)** are those events reported on the “Adverse Events Details” eCRF page, with the “Serious Adverse Event” field ticked “Yes”.

**Adverse Events Leading to Temporary Discontinuation** are those events leading to temporary discontinuation of study treatment (answer to the question “Action(s) taken with M7824” = “Drug interrupted” on “Adverse Event Details” eCRF page).

**Adverse Events leading to Permanent Treatment Discontinuation** are those events leading to permanent discontinuation of study treatment (answer to the question “Action(s) taken with M7824” = “Drug withdrawn” on “Adverse Event Details” eCRF page).

**Adverse Events leading to Death** are those events leading to death (as recorded on the “Adverse Event Details” eCRF page, change in grade = “No” and outcome = “Fatal”, or Grade = “Grade 5 or death related to AE” or Serious adverse event = “Yes” and seriousness criteria include “Results in death”).

**Adverse Events of Special Interest (AESI):** AESI are identified according to a pre-specified search list of MedDRA Preferred Terms (PTs). Categories of AESI include:

- Infusion-Related Reactions (IRRs)
- Immune-Related Adverse Events (irAEs)
- Skin AEs possibly related to TGF- $\beta$  inhibition
- Anemia

**Bleeding events** are those events belonging to the MedDRA SMQ Haemorrhage terms (excluding laboratory terms).

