## 6.9

### Management of Adverse Events of Special Interest and other Potential Risks

Adverse events of special interest (AESIs) are serious or non-serious AEs specific to the known mechanism of action of the study intervention that are of clinical interest requiring ongoing monitoring.

For this study, AESIs include the following:

- Infusion-related reactions including hypersensitivity
- Immune-related AEs
- TGF- $\beta$  inhibition mediated skin reactions
- Anemia
- Bleeding AEs

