## 6.9.5 Bleeding Events

Bleeding events are AESIs and considered an important identified risk for M7824 (refer to the IB).

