### Adverse Events of Special Interest

Infusion-related reactions including hypersensitivity, immune-related AEs, TGF- $\beta$  inhibition mediated skin reactions, anemia, and bleeding AEs are all considered as AESI for M7824.

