## Changes to the Planned Analyses in the Clinical Study Protocol

The statistical methods as described in the protocol were adopted. There are no changes to the planned analyses.

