### Evaluation of COVID-19 effects on AEs

The direct effect of COVID-19 for AEs will be assessed via listings of COVID-19 related AEs. The following listings will be generated using the ‘COVID-19 related terms MedDRA 23.0 update Spreadsheet’ (<https://www.meddra.org/covid-19-related-terms-meddra-230-update-spreadsheet>, last accessed on 28 May 2020) as available from Maintenance and Support Services Organization (MSSO), considering all ‘search terms for COVID-19-related’ =’Y’. The following information will be provided:

- Subject ID, country, age, sex, race
- Date of first, last treatment with study drug
- COVID-19-associated AE start date (day), COVID-19 associated AE stop date (day)
- AE preferred term, verbatim
- Toxicity grade
- Seriousness
- Relationship to treatment
- Action taken
- Outcome

The indirect effect of COVID-19 for AEs will be assessed based on the difference in incidence rate between subgroups of pre and during COVID-19 period according to categorization method with time window:

- For common TEAEs applying frequency threshold of 10% in either subgroup of pre/during COVID-19 period, butterfly plots displaying incidence rates of TEAEs NCI-CTCAE severity grade  $\leq 2$  and  $\geq 3$  will be provided.
- For each AESIs defined in Section 15.2.4 occurred on 4 or more participants in any subgroup (Rule-of-4), forest plots displaying incidence rates, differences in incidence rates as well as the CI for the difference will be provided.

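### The SAP does not classify bleeding as an AESI, although protocol 5.0 does, so no bleeding-specific serious or permanent-discontinuation count, listing, flag or COVID-19 comparison is planned

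*SAP*

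**What the plan says.** Protocol 6.9 opens its list with "For this study, AESIs include the following" and gives five categories: infusion-related reactions, immune-related AEs, TGF-β skin reactions, anemia and bleeding. Protocol 6.9.5 states "Bleeding events are AESIs and considered an important identified risk for M7824", and the AESI paragraph of Appendix 4 closes with "anemia, and bleeding AEs are all considered as AESI for M7824". The occurrence of TEAEs and related AEs, AESIs included, is a secondary endpoint (protocol Section 3; SAP Table 1). Protocol 9.4.2 asks that AESI incidence be summarized by preferred term (PT) and system organ class (SOC).

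SAP 15.1 writes "AESI are identified according to a pre-specified search list of MedDRA Preferred Terms (PTs). Categories of AESI include" and then lists the first four categories only. Directly after the list it defines bleeding as a separate group, using the MedDRA SMQ Haemorrhage without its laboratory terms. Section 15.2.3 covers bleeding and Section 15.2.4 covers the AESIs. SAP Section 7 says "There are no changes to the planned analyses".

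**The concern.** The two documents give one part of a secondary safety endpoint different content: five categories in the protocol, four in the SAP. This has practical effects, because several SAP outputs are tied to AESI status or to Section 15.2.4 and so pass bleeding by.

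The discontinuation count is of particular interest. Protocol 6.9.5.1 links Grade 3 and Grade 4 non-tumor bleeding to permanent discontinuation, subject to alternative explanations. The SAP reports bleeding by grade but plans no summary of how many participants stopped treatment because of it.

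**Working it through.** No formula or published figure is involved. The check compares what the SAP plans for each of the five protocol categories (SAP 15.1.1, 15.2.3 and 15.2.4.1 to 15.2.4.4).

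| Planned output | IRR | irAE | Skin | Anemia | Bleeding |
|---|---|---|---|---|---|
| Overview rows, all and related | yes | yes | yes | yes | yes |
| Own frequency table by term | yes | yes | yes | no | yes, by worst grade, all and related |
| Dedicated listing | yes | yes | yes | yes | no |
| Y/N flag in AE listings | yes | yes | yes | yes | no |
| Eligible for COVID-19 AESI plots | yes | yes | yes | yes | no |
| Count leading to permanent discontinuation | yes | yes | yes | no | no |
| Count of serious events | no | yes | yes | no | no |

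**What AESI status brings.** The listing, the flag and COVID-19 eligibility go to 4 of the 4 SAP AESIs. The permanent-discontinuation count goes to 3 of 4 and the serious count to 2 of 4. Bleeding has none of the five. The COVID-19 plots exclude it by section number: their condition begins "For each AESIs defined in Section 15.2.4 occurred on 4 or more participants in any subgroup (Rule-of-4", and bleeding sits in 15.2.3.

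**Whether general tables supply the two counts.** SAP 15.1.2 tabulates TEAEs leading to permanent discontinuation, and 15.2.2 tabulates serious AEs, both by SOC and PT. Under 15.1.1 a participant counts once within each PT or SOC. Protocol 6.9.5.1 gives epistaxis, hemoptysis, gingival bleeding and hematuria as examples, so bleeding is spread over several PTs. If two bleeding PT rows show a and b participants, the number with either lies anywhere from max(a, b) to a + b, so the rows cannot simply be added. SOC rows mix bleeding with other events.

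**Whether listings supply them.** They can. The general AE listings carry PT, seriousness and action taken, and there are listings of SAEs and of TEAEs leading to permanent discontinuation. Someone would have to match PTs to the SMQ by hand, because no bleeding flag is carried.

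**Timing.** SAP version 2 is dated 26 August 2020 and protocol 5.0 is dated 22 June 2021, about ten months later. The protocol 5.0 change table moves bleeding from potential risk to important identified risk and says the event lists in 6.9 and Appendix 4 were updated. SAP Section 9 puts the last participant's treatment start at 3 January 2020. Adding the 9 and 15 months of SAP Table 2 gives cut-offs of about 3 October 2020 and 3 April 2021, both before protocol 5.0.

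**The case against.** The best defense is that bleeding is already well served. It has overview rows for all and related events and its own section by SOC, PT and worst grade. That satisfies protocol 9.4.2, which does not ask for serious or discontinuation counts by AESI category. This stands. A reader might infer from the missing AESI label that bleeding receives no AESI-type reporting; the SAP shows otherwise, and bleeding is tabulated more fully than anemia.

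It is also fair to say that the label alone does not explain every gap. Anemia is a SAP AESI, yet 15.2.4.4 gives it only a listing, and the IRR summary has no serious row. So the missing serious and discontinuation counts do not follow automatically from the omission. The missing listing, flag and COVID-19 comparison do match what AESI status brings in every case.

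A reader might further conclude that the report could not say how many participants had serious bleeding or stopped because of it. That goes too far: the counts can be derived from the listings. What is absent is a planned, reproducible aggregate.

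Finally, one might call the no-changes statement in SAP Section 7 false. The documents do not show that bleeding was an AESI in the protocol in force in August 2020, so that reading is unsupported. The mismatch is better explained by a later reclassification that the SAP does not reflect. The COVID-19 plots are an added impact assessment, and leaving bleeding out of them touches no protocol objective.

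**Conclusion.** The point holds as a misalignment between the SAP and protocol 5.0. One of five protocol AESI categories is outside the SAP's AESI set. For that category, two participant counts, a dedicated listing, a flag and a COVID-19 comparison are not planned. Incidence by SOC and PT, worst grade and relatedness are unaffected, as are all efficacy analyses.

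It is worth correcting because bleeding is an important identified risk within a secondary endpoint, and because the general SOC and PT tables cannot be summed to give the counts. The conclusion assumes that SAP version 2, the last in its modification history, is the plan in use, and that protocol 5.0 governs the AESI definition for reporting.

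**What to change.** - In SAP 15.1, add bleeding events to the AESI list with the existing definition (SMQ Haemorrhage, laboratory terms excluded), and add a bleeding subsection to 15.2.4.
- State expressly that the 15.2.3 table by SOC, PT and worst grade is kept, for all and related events. SAP 15.1.1 exempts AESIs from its SOC and PT frequency tables, so relabeling bleeding without this sentence could remove output that the protocol requires.
- Add participant counts of serious bleeding and of bleeding leading to permanent discontinuation, a bleeding listing, and a Y/N flag in the AE listings.
- Include bleeding in the COVID-19 AESI plots.
- Record the change in the SAP modification history. If outputs have already been produced, add these and identify them in the study report as additions aligning with protocol 5.0; SAP Section 4 already requires unplanned analyses to be identified there.

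The cost is SAP wording, one extra summary table and one listing, plus a flag column and an added entry in the plots. No new data are needed: the search definition is in the SAP, and seriousness and action taken are already recorded on the AE page of the eCRF.

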### 15.1.1 All Adverse Events

Adverse events will be summarized by worst severity (according to National Cancer Institute - Common Terminology Criteria for Adverse Events [NCI-CTCAE] version 5.0) per participant, using the latest version of MedDRA preferred term (PT) as event category and MedDRA primary system organ class (SOC) body term as Body System category.

Unless otherwise stated adverse events will be displayed in terms of frequency tables: PTs and primary SOCs in alphabetical order.

Each participant will be counted only once within each PT or SOC. If a participant experiences more than one AE within a PT or SOC for the same recording period, only the AE with the strongest relationship or the worst severity, as appropriate, will be included in the summaries of relationship and severity.

If an adverse event is reported for a given participant more than once during treatment, the worst severity and the worst relationship to study treatment will be tabulated. In case a participant had events with missing and non-missing grades, the maximum of the non-missing grades will be displayed.

A table presenting the overall summary of AEs will be presented including the frequency (number and percentage) of participants within each of the following categories:

- TEAEs
- Related TEAEs
- Serious TEAEs
- Related Serious TEAEs
- TEAEs NCI-CTCAE severity grade ( $\geq 3, \geq 4$ )
- Related TEAEs NCI-CTCAE severity grade ( $\geq 3, \geq 4$ )
- TEAEs leading to death
- Related TEAEs leading to death
- AEs and related AE of special interest:
  - Infusion-related reactions (IRRs)
  - Immune-related AEs (irAEs)
  - Potential TGF- $\beta$ -mediated skin AEs
  - Anemia
- TEAE, bleeding events
- Related TEAEs bleeding events

Tables for TEAEs frequency corresponding to each category in the overview table above will be provided by:

- MedDRA primary SOC (ordered alphabetically) and PT (ordered alphabetically), (except for AE of special interest)

TEAEs and related TEAEs by worst grade will also be summarized, and the most frequent PT (at least 5%) will be presenting graphically by worst grade and PT with bar chart figures.

### Clinicaltrials.gov and EudraCT -requirements

Summary table for non-serious TEAEs excluding SAEs applying frequency threshold of 5% will be provided.

Listings of adverse events will contain the following information: participant identifier, age, sex, race, first and last date of study intervention, preferred term, reported term for the AE, start date, end date, duration of AE (in days), day relative to the first infusion, day relative to the most recent infusion prior to AE onset, relationship to study treatment, toxicity grade, action(s) taken, outcome, seriousness (Y/N), AESI infusion-related (Y/N), AESI immune-related (Y/N), potential TGF- $\beta$ -mediated skin AESI (Y/N), anemia AESI (Y/N). TEAEs and AEs occurring during the re-initiation period will be flagged.

Following listings will be provided with the relevant information:

- Listing of all AE (whether treatment-emergent or not) (TEAEs will be flagged) (AE occurring during re-initiation phase will be flagged)
- Listing of TEAEs
- Listing of non-TEAE for AEs occurring after enrollment (date of first signature of informed consent/date of first signature of first informed consent) but prior to the first dose of study intervention.
- Listing of AE with onset or worsening after the on-treatment period (AE occurring during re-initiation phase will be flagged)
- Listing of AEs for participants who reinitiated the treatment

### Evaluation of Potential Effect of ADA and nAb on bintralusp alfa Safety

The following analyses frequency and percentage of AEs by ADA status (ever positive, never positive), and by nAb status (ever positive for either assay, never positive) will be performed:

- TEAEs
- TEAEs, grade  $\geq 3$
- TEAEs leading to permanent treatment discontinuation
- TEAEs excluding IRRs leading to drug interruptions
- Serious TEAEs
- TEAEs leading to death
- irAEs (see definition in Section 15.2.4.2)
- IRRs (see definition in Section 15.2.4.1)

This will be repeated for Japanese participants.

Listings of all AEs and all IRRs for ever-positive ADA participants (pre-existing, transient treatment-emergent, persistent-treatment emergent) will be prepared including participant identifier and showing the date(s) of the positive ADA result together with the AEs or IRRs. For the AEs and IRRs, start and stop date will be shown along with grade. Adverse events recorded during the period of 2-weeks prior to the positive ADA value till two weeks after the positive ADA value will be flagged. This will be repeated for ever-positive nAb participants in either assay (PD-L1 and TGF- $\beta$ ). These analyses for ever positive ADA and ever positive nAb subjects in either assay will be repeated for Japanese participants.

